- M:** During the fixed-dose Treatment Period 1, subjects who experience very frequent HAE attacks (ie, \geq 12 attacks, as defined per protocol, within a 4-week evaluation period) are eligible for CSL830 dose increases in increments of 20 IU/kg (up to a maximum dose of 80 IU/kg). All CSL830 dose increases are optional, and will be made only in subjects who are eligible, at the sole discretion of investigator. An evaluation period for any dose increase is defined as beginning after a dose-stable period (ie, 2 weeks after the initiation or dose increase of CSL830). See [Section 3.2](#) for additional details.
- N:** Beginning with the Week 25 Visit and throughout Treatment Period 2, subjects who experience \geq 3 HAE attacks (as determined per protocol) within an 8-week evaluation period are eligible for CSL830 dose increases in increments of 20 IU/kg (up to a maximum dose of 80 IU/kg). All CSL830 dose increases are optional, and will be made only in subjects who are eligible, at the sole discretion of investigator. An evaluation period for any dose increase is defined as beginning after a dose-stable period (ie, 2 weeks after the initiation or dose increase of CSL830). See [Section 3.2](#) for additional details.

O: The subject eDiary will not be collected from subjects at the last visit of Treatment Period 2 (Follow-up Visit) if they plan to participate in the Extension Period.

Schedule of Laboratory Assessments for “CSL830-Interrupted” Subjects ^A and “CSL830-Naïve” Subjects ^B

	Screening	Treatment Period 1								Treatment Period 2						Follow-up ^C	
Week	-4 to -1	1	5	9	13	17	21	25	29	33	37	41	45	49	53	See Footnote C.	
Day	-28 to -1	1	4	29	57	85	113	141	169	197	225	253	281	309	337		367
Window (days)		+ 1	± 2	± 2	± 2	± 2	± 2	± 2	± 2	± 2	± 2	± 2	± 2	± 2	± 2		± 2
Study center visit	X	X	X		X		X		X	X		X		X		X	X
Telephone contact				X		X		X			X		X		X		
Blood samples: • Hematology • Biochemistry • Coagulation		X			X				X	X		X					X
CCI [REDACTED]	X ^E	X			X				X	X		X					X
Blood sample for anti-C1-INH antibody		X							X								X
Blood sample for viral serology		X							X								X
Urine sample for urinalysis		X			X				X	X		X					X
Urine sample for pregnancy test ^D		X			X				X			X					X

C1-INH = C1-esterase inhibitor; CCI [REDACTED]; [REDACTED].

Notes to the Schedule of Laboratory Assessments for “CSL830-Interrupted” Subjects and “CSL830-Naïve” Subjects:

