1.4 Potential Risks and Benefits

Potential for Virus Transmission

CSL830 contains human plasma-derived C1-INH and, therefore, has the potential for virus transmission to recipients. However, CSL830 has a high margin of virus safety. The risk of virus transmission is minimized by stringent donor selection and screening criteria, and by reducing enveloped and non-enveloped viruses using pasteurization, nanofiltration methods, and chromatography [De Serres et al 2003].

During study CSL830_2001 (see [Section 1.2.3](#)), no new viral infections were detected in subjects who received CSL830. No changes in serology results for HIV (human immunodeficiency virus), hepatitis A virus, HBV (hepatitis B virus), HCV (hepatitis C virus) were observed from baseline to study exit.

During this 12-month safety study, evidence of potential viral transmission will be collected as part of the safety evaluations.

Immunogenicity or Anaphylactic-type Reactions

Immunologic or anaphylactic-type reactions have been rarely reported with the use of C1-INH. Antibodies against C1-INH have been identified in patients with HAE, irrespective of whether they have received C1-INH. However, the presence of antibodies against C1-INH does not appear to inhibit the activity of C1-INH [data on file at CSL; [Farkas et al 2007](#)].

The immunogenicity of CSL830 was examined as a part of study CSL830_2001 (see [Section 1.2.3](#)). C1-INH antibodies were detected for 7/18 subjects during that study; however, the presence of C1-INH antibodies was not associated with inhibition of C1-INH activity. There was no apparent relationship between the dose of CSL830 administered and the presence of C1-INH antibodies.

The development of immune reactions to CSL830 will be monitored in this study, and will include testing for and characterization of (eg, idiotyping) anti-C1-INH antibodies.

Thromboembolic Events

Thromboembolic events have been occasionally reported following the use of C1-INH, especially in patients receiving off-label high doses of up to 500 U/kg IV in the setting of cardiac surgery and extracorporeal circulation. At the recommended IV doses, a causal relationship between TEEs and the use of C1-INH has not been established.

During study CSL830_2001 (see [Section 1.2.3](#)) no TEEs were reported. Further, no subject treated with CSL830 was considered to be at risk for DVT, when assessed using a clinical model scoring system.

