Urine Pregnancy Test ^A
Confirm Access to On-demand HAE Medication
CSL830 Accountability
Concomitant Medication
Adverse Events

Abbreviations: DVT = deep vein thrombosis; HAE = hereditary angioedema; PE = pulmonary embolism.

^A The results of the urine pregnancy test can only be used to satisfy the applicable eligibility criterion if the Treatment Period 2 End of Study Visit and the first visit of the Extension Period (ie, Day 367) occur on exactly the same day. Otherwise, a new pregnancy test must be performed at the first study visit in the Extension Period in order to confirm eligibility.

8.4.6.2 Extension Period Week 6

Subjects will be contacted by telephone at the Extension Period Week 6 Visit (± 2 days) to record AEs and concomitant therapies and self-administer the AE QoL questionnaire.

8.4.6.3 Extension Period Week 12

Subjects will attend a study visit at Extension Period Week 12 (± 2 days).

The following procedures will be performed by the investigator or delegate:

- Vital signs including weight.
- Assess risk of DVT and PE.
- CCI [Redacted]
- CCI [Redacted]
- CCI [Redacted]
- CCI [Redacted]

- [REDACTED]
- Review subject eDiary; record information on HAE attacks in eCRF.
 - Perform CSL830 accountability.
 - Confirm access to on-demand medication for the treatment of breakthrough HAE attacks.
 - Record AEs.
 - Record concomitant therapies.
 - Dispense CSL830/study supplies to subject.
 - Schedule the next telephone contact and the next study visit.

8.4.6.4 Extension Period Week 18

Subjects will be contacted by telephone at the Extension Period Week 18 Visit (± 2 days) to record AEs and concomitant therapies.

8.4.6.5 Extension Period Week 22

Subjects will self-administer the AE QoL questionnaire at Extension Period Week 22 (± 2 days).

8.4.6.6 Extension Period Week 24

Subjects will attend a study visit at Extension Period Week 24 (± 2 days).

The following procedures will be performed by the investigator or delegate:

- Vital signs including weight.
- Physical examination.
- Assess risk of DVT and PE.
- Obtain blood sample for assessment of antibodies against C1-INH.
- For female subjects, obtain urine sample for dipstick pregnancy testing.
- Review subject eDiary; record information on HAE attacks in eCRF.
- Perform CSL830 accountability.
- Confirm access to on-demand medication for the treatment of breakthrough HAE attacks.
- Record AEs.
- Record concomitant therapies.
- Dispense CSL830/study supplies to subject.

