2.1 Primary endpoints

The primary endpoints are the person-time incidence rates of each of the following:

- Adverse events (AEs) leading to premature study discontinuation.
- Thromboembolic events (TEEs).
- Anaphylaxis.
- HAE attacks resulting in in-patient hospitalization.
- Solicited AEs (injection site reactions at the CSL830 injection site) graded as severe by the investigator.
- Related serious AEs (SAEs), other than events specified above.
- Anti-C1-esterase inhibitor (C1-INH) antibodies (inhibitory or non-inhibitory).

For each primary endpoint safety event, the person-time incidence rates are calculated as:

- the number of subjects experiencing the primary endpoint safety event at least once during treatment with CSL830, divided by the sum of each subject's time at risk

and

- the total number of the primary endpoint safety events divided by the sum of each subject's time at risk.

Further details how the number of subjects experiencing the primary endpoint safety event, the number of the primary endpoint safety events and the time at risk will be calculated are outlined in [Section 4.7.1](#).

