3.3 Study Schedule

3.3.1 Planned study duration

The duration of the study for an individual subject who does not participate in the Extension Period is expected to be up to 58 weeks. This estimation is based on:

- A Screening Period lasting up to 4 weeks (≤ 28 days), as needed.
- Two treatment periods totaling 52 weeks (367 days \pm 2 days).
- A Follow-up Period lasting 2 weeks (14 days \pm 3 days).

The overall study duration (i.e., from the first subject's first Screening Visit to the last subject's Follow-up Visit) is planned to be 26 months, but will depend on recruitment.

US-subjects will have the opportunity beyond the Week 53 Visit to enter into an Extension Period of up to 90 weeks. The Extension Period will comprise a treatment period of 88 weeks and a follow-up period of 14 days \pm 3 days (see Country-Specific Protocol Amendment No. 1 (United States), dated 10 July 2015).

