4.7.1 Primary Safety Analysis

Primary safety endpoints are listed in [Section 2.1](#).

The date of study completion is defined for the safety analyses as the (latest) Follow-up Visit. If a subject discontinued from the study, the date the subject came back to site for a final

study visit will be entered as the date of study discontinuation (to be entered as Week 53 Visit for subjects not taking part in the Extension Period and to be entered as Week 88 Visit for subjects taking part in the Extension Period) or if no further study visit takes place, the date when the subject informed the investigator. The study completion or study discontinuation (whichever applies for the individual subject) is considered as the end of treatment date.

The person-time incidence rates will be calculated in two different ways:

- For the number of subjects experiencing a particular event (bullet points i. below),
- For the number of experienced events (bullet points ii. below).

These 2 analyses approaches for the primary safety endpoints are conducted using 3 different approaches for the selection of the treatment groups which are included in the respective analyses. The following treatment groups will be regarded:

- 1) Treatment, as treated, up until CSL830 dose increase, or either CSL830 discontinuation or study completion – whichever comes first.
- 2) Treatment, as treated at the time of randomization, up to CSL830 discontinuation or study completion – whichever comes first.
- 3) Actual treatment.

In total, six analyses will result and the person-time incidence rates will be calculated

for 1) as

- i. the number of subjects experiencing a given primary endpoint safety event during the treatment duration with CSL830 up until the time of CSL830 dose increase or either CSL830 discontinuation or study completion (whichever is first), divided by the sum of each subject's time at risk. The "time at risk" (in years) is calculated per subject as:

(Date the subject experiences the first event or a CSL830 dose increase or either CSL830 discontinuation or study completion (whichever is first) – date of the subject's first injection of CSL830 in treatment + 1) / 365.25.

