- i. the number of subjects experiencing a given primary endpoint safety event during treatment with an actual dose of CSL830 divided by the sum of each subject's time at risk while receiving that actual dose of CSL830. The "time at risk" (in years) is calculated per subject as:

(Date the subject experiences the first event, a CSL830 dose increase, or either CSL830 discontinuation or study completion (whichever is first) while taking a given, actual dose of CSL830 – date of the subject's first injection of the given, actual dose of CSL830 + 1)] / 365.25.

- ii. the sum of each subject's total number of events of a given primary endpoint safety event during treatment with an actual dose of CSL830 divided by the sum of each subject's time at risk while receiving that actual dose. The "time at risk" (in years) is calculated per subject as:

(Date the subject undergoes CSL830 dose increase or either CSL830 discontinuation or study completion (whichever is first) while taking the given, actual dose of CSL830 – date of the subject's first injection of the given, actual dose of CSL830 + 1)] / 365.25.

A subject accrues events over the time during which that subject receives a given actual CSL830 dose while participating in the study. If a subject undergoes a dose increase during the study and that subject experiences events during treatment with each respective dose of CSL830, such a subject contributes events in each treatment received. A subject randomized to 40 IU/kg and up-titrated to 60 IU/kg will be displayed in both treatments as well as in the ≥ 40 IU/kg treatment based upon their corresponding duration in that treatment.

The 95% CI will be calculated for each of the above described person-time incidence rates using the following formula:

$$\text{Lower CI} = \frac{k}{T} \chi^2(2 * Y, 0.025)/2$$

$$\text{Upper CI} = \frac{k}{T} \chi^2(2 * Y + 2, 0.975)/2$$

with

k = factor to normalize for annual rate which is equal to 1

T = sum of time at risk [years] over subjects calculated as described in the bullet points above.

For the person-time incidence rates described above in i.:

Y = number of subjects who experienced the safety event

For the person-time incidence rate described above in ii.:

Y = number of safety events

A by-subject listing will be produced showing the information if a subject has each primary endpoint safety event.

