4.12 Handling of Missing Data

No imputation is planned. The primary safety endpoints are the person-time incidence rates of each primary endpoint safety event which are already taking into account that subjects' observation times can differ between subjects. Subjects receiving study drug will always have a certain amount of observation time and so will always contribute data/information to the primary safety endpoint independent if they discontinue early from the study or not. Only if a subject drops out before receiving any study drug this will lead to missing data for this subject, but this subject would not be included in the Safety Population anyway.

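### Time at risk for the primary anti-C1-INH antibody rate is not tied to antibody samples, so starting-dose rates are understated and the comparison between doses can be distorted

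*SAP*

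**What the plan says.** Anti-C1-INH antibodies, inhibitory or not, are one of the seven primary person-time rates (Protocol 2.1.2, SAP 2.1). SAP 4.7.1 defines time at risk once for all seven. In the actual-treatment analysis (approach 3) the subject-based rate stops at "Date the subject experiences the first event, a CSL830 dose increase, or either CSL830 discontinuation or study completion", whichever is first. Approach 1 uses the same stopping points for the starting dose and drops later events. Approach 2 ignores dose increases and attributes everything to the starting dose. For safety, "The date of study completion is defined for the safety analyses as the (latest) Follow-up Visit". None of these formulas refers to a sample date.

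The row "Blood sample for anti-C1-INH antibody" in the protocol's laboratory schedules is marked at Day 1, Week 25 and Week 53 only. The visit lists agree (Protocol 8.4.3.8 and 8.4.4.7), and the Follow-up Visit has no blood draw (8.4.5.1). In the Extension Period the visit lists place the antibody sample at Weeks 24, 48, 72 and 88; Week 24, for example, reads "Obtain blood sample for assessment of antibodies against C1-INH". At withdrawal, the Week 53 or Extension Week 88 assessments are to be attempted (Protocol 4.2.2).

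SAP 4.12 plans no imputation, on the ground that a subject who receives study drug "will always contribute data/information to the primary safety endpoint" whether or not they discontinue early.

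**The concern.** The 4.12 statement suits clinical events, which can be reported on any day. It does not suit a laboratory result. A subject who leaves before Week 25 without an exit sample has no post-baseline antibody result, yet adds person-time as if observed to be event-free. The same holds for time between the last sample on a dose and the end of time at risk on it.

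Dose increases add a second problem. A conversion that happens before an increase but after the last sample is found only at the next sample, when the subject is on the higher dose. Approach 3 then charges it to the higher dose. The lower dose keeps the time and loses the event. At stake are a primary immunogenicity rate, its confidence interval, and any reading of that rate by dose.

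**Working it through.** The plan gives no expected antibody rate to reproduce. Its only calculated figure, the sample-size statement in SAP 3.8, reproduces (1 − 0.97^100 = 0.952) but does not bear on this point.

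**Inputs from the documents.** Samples on Days 1, 169 and 367. Follow-up Visit 14 ± 3 days after Day 367. Last Extension sample on Extension Day 617 and follow-up contact on Extension Day 631. About 110 randomized, up to 10% withdrawing, about 50 entering the Extension (Protocol 3.5). Fewer than 20% with a dose increase (SAP 4.14). Days at risk = end date − first injection + 1.

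**Follow-up time.** Non-extension completer: 14/381 = 3.7% of time lies after the last sample (11/378 = 2.9% to 17/384 = 4.4% over the window). Extension completer without a rest period: 14/(366 + 631) = 14/997 = 1.4%.

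**One dose increase on day d, non-extension completer.** The unsampled share of starting-dose time is (d − 169)/d. For the dose after the increase in approach 3, a low constant rate and persistent antibodies give reported/true ≈ days of conversion charged to that dose ÷ its days at risk = (367 − 169)/(381 − d + 1).

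| Increase at | Unsampled share of starting-dose time | Reported/true, dose after increase |
|---|---|---|
| Before Week 25 | 100% | – |
| Week 25 (Day 169) | 0/169 = 0% | 198/213 = 0.93 |
| Week 29 (Day 197) | 28/197 = 14% | 198/185 = 1.07 |
| Week 37 (Day 253) | 84/253 = 33% | 198/129 = 1.53 |
| Week 45 (Day 309) | 140/309 = 45% | 198/73 = 2.71 |

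The Week 25 row assumes that the sample taken that day belongs to the starting dose. The overstatement is smaller for Extension completers: for a Week 45 increase, (983 − 169)/(997 − 309 + 1) = 814/689 = 1.18.

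A subject increased twice, at Weeks 25 and 37, 25 and 45, or 29 and 45, spends 84, 140 or 112 days on 60 IU/kg with no sample after the visit of the first increase.

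**Pooled approach 1 denominator.** Assumed, not in the documents: 11 of 110 withdraw at Day 120, half of them sampled at exit; 11 subjects increase at Week 29 (low case) or 22 at Week 45 (high case).

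- Low: total 88×367 + 11×197 + 11×120 = 35,783 days; sampled 88×367 + 11×169 + 5.5×120 = 34,815; excess 2.8%.
- High: total 77×367 + 22×309 + 11×120 = 36,377; sampled 77×367 + 22×169 + 5.5×120 = 32,637; excess 11.5%.
- With 50 Extension subjects, assumed to have no increase, add 50×617 = 30,850 days to each sum: 66,633/65,665 gives 1.5% and 67,227/63,487 gives 5.9%.
- Follow-up time of completers adds 88×14/34,815 = 3.5 or 77×14/32,637 = 3.3 points without the Extension, and 1.9 or 1.7 points with it.

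**Approach 2, same withdrawals.** (99×367 + 11×120)/(99×367 + 5.5×120) = 37,653/36,993, an excess of 1.8%. With the Extension it is 68,503/67,843, or 1.0%. Both exclude follow-up.

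**Simulation, Treatment Periods 1 and 2 only.** Assumptions: constant hazard of 0.03, 0.10 or 0.30 per year, persistent antibodies, all subjects negative at baseline, up to 20% with one increase spread evenly over Weeks 25, 29, 37 and 45, and up to 10% dropout with none to all lacking an exit sample. Reported/true rate:

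- approach 2: 0.88 to 0.96;
- approach 1 with 20% increased: 0.85 to 0.93;
- starting-dose time of the increased subjects alone: 0.70 to 0.73;
- dose after the increase in approach 3: 1.20 to 1.34.

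These ratios also include the smaller downward effect of dating a conversion at the sample that finds it.

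**The case against.** A reader might infer that the antibody rate is simply biased low, chiefly because of dose increases. The documents do not support that. In approach 2, and in the ≥ 40 IU/kg column of approach 3, an increase loses nothing; only follow-up time and unsampled dropouts matter there. In approach 3 the final, higher dose tends to be overstated. Gaps between samples are largely recovered if antibodies persist.

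A reader might also take the earlier study's result, "C1-INH antibodies were detected for 7/18 subjects during that study", as proof that new antibodies will be common. Protocol 1.4 adds that such antibodies occur in HAE patients whether or not they have received C1-INH, so 7/18 is not shown to be an incidence. SAP 2.1 does not restrict the endpoint to new positives either. Counting Day 1 positives would raise the rate, so even the net direction is open.

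Other mitigation stands. Joint analysis with the Extension roughly halves the pooled excess. An increase before Week 25 requires at least 12 attacks in 4 weeks, so the 100% case should be uncommon. The high case puts 22 of 110 (20%) at Week 45, just above the SAP's own ceiling. When an exit sample is taken at the final visit, time at risk already ends there. SAP 4.7.2.3 also summarizes antibody status by visit, which avoids the person-time problem. The rates are descriptive, with no test or stopping rule attached.

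None of this makes the 4.12 statement true for antibodies, corrects the primary rate and its interval, or says to which dose a positive found after an increase belongs.

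**Conclusion.** The point holds in limited form. For this one endpoint the denominator includes time, and possibly whole subjects, in which no event could be recorded. In approaches 1 and 3 that understates the starting-dose rate. In approach 3 it is joined by misattribution, which tends to overstate the dose after the increase and could create or exaggerate a dose trend.

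The overall size is modest. The pooled approach 1 denominator is about 1.5% to 6% too large with the Extension and 3% to 11% without it, plus about 2 to 3.5 points for follow-up. These ranges rest on the assumed withdrawal day, exit sampling and timing of increases; the simulated ratios rest on persistent antibodies and negative baselines. The distortion by dose can be larger than the pooled figure, but concerns the minority of subjects whose dose is increased. The change should be made because it is cheap and affects a primary result; it does not threaten the trial.

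**What to change.** Amend SAP 4.7.1 for the antibody endpoint only:

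1. Include only subjects with at least one post-baseline antibody sample. End time at risk at the first positive or, failing that, the last antibody sample; in approach 1, use the last sample on the starting dose.
2. In approach 3, credit a dose only with sampling intervals that lie wholly on that dose. Count intervals that span a dose increase, and any positive first found in them, only in the ≥ 40 IU/kg column. Without this rule, step 1 would shorten the denominator of the higher dose and worsen its overstatement. State also to which dose a sample taken on the day of an increase belongs: SAP 4.4.1 ends exposure the day before the increase, while 4.7.1 uses the date of increase.
3. Treat only subjects negative at Day 1 (or at the final CSL830_3001 sample that replaces it) as at risk of a new event, and report Day 1 positives separately.
4. Report the number of treated subjects with no evaluable sample per dose, and limit the 4.12 sentence to endpoints that do not depend on a sample.

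This needs SAP wording and derived dates from data already collected. The cost is slightly less person-time and a slightly wider confidence interval for this endpoint.
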